This is a pilot study that is exploratory in nature and one of its goals is to collect preliminary data for multiple outcomes that may be used in future studies on the brain effects of CR.

For the primary and each secondary scalar measure, a separate repeated measures mixed models analysis will be conducted to examine the effects of the between-subjects factor “Group” (5-2 CR group vs. “Healthy living” control group), the within-subjects factor “Time” (Baseline vs. Outcome) and their Interaction. An Auto-Regressive (AR)1 covariance matrix and Restricted Maximum Likelihood Estimation (REML) will be used. We will assess fit to the model using the AIC and BIC criteria (lower values indicate better fit). These parameters were chosen because they are recommended for repeated measures analyses, including fMRI task analyses.¹⁰⁰ Regarding within-subjects effects, we will assess post-hoc differences between the 8-week outcome visit and baseline for the 5-2 CR and control groups and for each group separately (i.e. post-hoc tests for the Group * Time interaction). This analytic approach is common in the CR literature.¹⁰¹ Mixed model post-hoc tests will employ the Least Significant Difference (LSD) statistic. We will use one-tailed t-tests.

Criteria for significance will be set at alpha of 0.05 for all non-MRI analyses, and 0.005 uncorrected at the voxel level for fMRI analyses. Given that this pilot study is exploratory, we will not conduct correction of multiple comparisons for the various secondary outcomes.

Analysis of fMRI data will use a mixed model design to assess the effect of Group on

brain activation associated with viewing appetitive vs. non-appetitive food, the Stroop effect in the Stroop task, and DMN intrinsic functional connectivity. Analyses will be conducted at the whole brain level and within ROIs (vmPFC, OFC and insula for the fMRI food task, lateral and dmPFC for the Stroop task, and in DMN for resting state. The fMRI analyses will be corrected for type 1 error as the cluster level using Monte Carlo simulations.

For brain MRS measures, a repeated measures analysis will be separately used for each of the brain regions of interest: the hippocampus and the prefrontal cortex.

APOE genotype is a common covariate used when assessing populations with AD or at risk for AD. We intend to perform exploratory analyses including APOE, which may reduce error variance and improve our statistical models.

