Regarding our primary outcome (exosomal p-Ser312-IRS-1/p-panY-IRS-1), in our published study, we examined differences between preclinical samples from participants who eventually developed AD (92.1 ± 7.7) and controls (14.7 ± 0.9)⁵¹. We base our power analysis on the assumptions that the our subjects at high risk for AD had intermediate high values for p-Ser312-IRS-1/p-panY-IRS-1 ratio at baseline (ratio = 46), that the 5-2 CR intervention had a similar modest effect size as for peripheral IR in decreasing the ratio (0.3), whereas the control intervention induced no change. We used the following input parameters to determine power for ANOVA repeated measures, between-within interactions: $\alpha = .05$ (one tailed); 2 groups (5-2 CR vs. Healthy Living diet); 2 repeated measures (Baseline vs. Outcome); correlation between repeated measures = 0.4. Based on these parameters, we achieve over 90% power with a total 40 participants (see Figure 4 below for post-hoc power calculation (achieved power, given certain N and effect size)). These calculations are conservative (e.g. the effect size may be greater than 0.3); therefore, it is likely that we will actually achieve greater power in this study.

[figure not shown]

Figure 4. Post-hoc power calculation for primary outcome (exosomal p-Ser312-IRS-1/p-panY-IRS-1) analyzed with ANOVA for repeated-measures for within-between interaction. The x-axis depicts total sample size and the y-axis depicts Power.

In addition, we performed power calculations for several key secondary outcomes of interest.

Regarding fMRI, we performed power calculations based on a series of equations by Mumford and Nichols¹⁰⁰ that take into account the unique nature of fMRI data. We use an alpha = .005 for fMRI analyses, as recommended by Mumford and Nichols.

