Memory and Executive Function: Witte and colleagues⁶⁵ examined aged participants divided into groups that either engaged in 3 months of moderate (30%) CR ($n=20$), received no intervention ($n=10$), or received unsaturated fatty acid supplementation ($n=20$). For the Rey Auditory Verbal Learning Test, which is very similar to our CVLT, CR participants showed a significant 130% gain (Cohen's $d = 0.799$) in a composite memory score after the intervention versus non-significant changes in the other groups. Our own intervention only differs in the length of time spent on CR and the intermittent nature of the CR, and so we anticipate a comparable effect size. Given that executive function is more consistently impacted by obesity and by extension IR across the lifespan,^{105,106} we also anticipate a similar or greater effect size for executive function, although there are currently no studies in the literature directly comparable to our design. In summary, with an anticipated effect size $f = 0.4$, we will have power = 0.81 to detect an effect on cognition.

Plasma biomarkers: For plasma biomarkers, such as proinflammatory cytokines, ROS, BDNF, and affect measures, we note that our previous within-subjects study on intermittent CR in humans³⁹ produced robust differences in significant or near-significant trends in these measures by 3 mo. with $n = 42$ at alpha = .05. We anticipate being able to detect such effects and more subtle differences, because our between-subjects design is more powerful. In particular, informal power calculations suggest that we will have at least 80% power to detect differences in cytokines, ROS, and BDNF.

Global gene expression and genome-wide methylation: With sample size of 20 for each of the two groups, using the Illumina HT12 expression chip with 25,000 annotated genes, there is 80% power at alpha (two-tailed) = 0.05 to detect a 1.5-fold difference in expression. Similarly, with the sample size of the proposed study, we have 90% power to detect methylation differences of 40% between groups at alpha (two-tailed) = 0.05 for 45,000 CpG sites.

11. Human subjects protection

11. a. Subject selection

Statement of equitability

Participants will be recruited and enrolled equitably including, but not limited to,

without regard to race, ethnicity, sex, sexual orientation, unless explained below.

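### The over-90% power for the primary outcome is power for a 1.2-SD between-arm difference in change, which section 10.b calls modest on an effect-size scale it never defines

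*Combined protocol and SAP*

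**What the plan says.** Section 10.b takes f = 0.440 for peripheral insulin sensitivity from a cited 12-month calorie-restriction trial and lowers it to 0.3 for 8 weeks of 5-2 CR. It carries that value over to the primary outcome by assuming that "the 5-2 CR intervention had a similar modest effect size as for peripheral IR in decreasing the ratio (0.3"), with no change in the control arm. The G*Power inputs are alpha .05, "one tailed); 2 groups (5-2 CR vs. Healthy Living diet); 2 repeated measures (Baseline vs. Outcome); correlation between repeated measures = 0.4". The Figure 4 caption describes the outcome as "analyzed with ANOVA for repeated-measures for within-between interaction". The result is "Based on these parameters, we achieve over 90% power with a total 40 participants". The text then adds "These calculations are conservative (e.g. the effect size may be greater than 0.3") and says that greater power is likely.

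Further on in 10.b, for memory and executive function, the plan cites d = 0.799, anticipates f = 0.4 and says "we will have power = 0.81 to detect an effect on cognition".

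Section 10.a sets the decision rule: "Criteria for significance will be set at alpha of 0.05 for all non-MRI analyses" and "We will use one-tailed t-tests".

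**The concern.** Two things do not fit together. First, at the same 40 participants, the smaller effect (f = 0.3) is given more power than the larger one (f = 0.4). One method on one scale cannot do that. Second, f has no fixed meaning until the test is named. In a 2 x 2 within-between interaction, a value that looks modest corresponds to a large difference between arms.

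This is the only power statement for the primary outcome, and section 2.a frames the primary objective as demonstrating a significant effect against controls. Anyone reading a null result will take from 10.b that a modest effect would almost certainly have been found. If the figure in fact refers to a difference above one SD, that inference fails.

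**Working it through.** **Inputs.** All from 10.b unless noted: N = 40 completers, 20 per arm; m = 2 visits; correlation rho = 0.4; alpha 0.05, one-tailed (also 10.a); f = 0.3. Withdrawals are replaced until 40 complete, so no dropout adjustment is needed.

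**1. Reproduce the plan's figure.** With G*Power's default for the within-between interaction:

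- lambda = f² × N × m / (1 − rho) = 0.09 × 40 × 2 / 0.6 = 12
- F(1, 38) at alpha 0.05: power 92.2%
- One-sided t with 38 df and noncentrality √12: power 96%

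So the stated figure follows from the inputs. A simulation with 40,000 replicates gave 92.5% and 96.3%.

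**2. Translate f = 0.3 into a difference between arms.** In a 2 x 2 interaction the four cell effects are ± (difference in change)/4, and f is that quantity divided by the outcome SD.

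- Difference in change = 4 × 0.3 = 1.2 outcome SD
- SD of change = √(2 × (1 − 0.4)) = √1.2 = 1.095 outcome SD
- Difference in SD of change = 1.2 / 1.095 = 1.10

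A two-sample t-test on change scores with this difference and 20 per arm gives the same 92% (two-sided) and 96% (one-sided).

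**3. What 20 per arm can detect.** Two-sample noncentral t on change:

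| Power | One-sided 0.05 | Two-sided 0.05 |
|---|---|---|
| 80% | 0.80 SD of change (× 1.095 = 0.88 outcome SD) | 0.91 SD of change (1.00 outcome SD) |
| 90% | 0.94 SD of change (1.03 outcome SD) | 1.05 SD of change (1.15 outcome SD) |

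Over 90% power therefore needs a difference above one outcome SD, whichever sidedness is used.

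**4. Compare with the cognition statement.**

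- Primary outcome's method at f = 0.4: lambda = 0.16 × 80 / 0.6 = 21.3, power 99.4%. The plan states 0.81.
- On f = d/2, 0.799 / 2 = 0.40. A one-sided two-sample t at d = 0.799 with 20 per arm gives 79.9%; the normal approximation at d = 0.8 gives 81.2%.
- A repeated-measures between-factor test with correlation 0.5 (an assumed value) also gives 81.2%.

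So the 0.81 can be matched on a different scale or with a different test, but not with the method used for the primary outcome.

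**5. Sensitivity: if 0.3 was meant as d/2.** Then d = 0.6, and with 20 per arm:

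| 0.6 measured in | One-sided | Two-sided |
|---|---|---|
| SD of change | 59% | 46% |
| Outcome SD (0.6 / 1.095 = 0.55 SD of change) | 52% | 39% |

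**6. Do the documents settle the scale?** No. For the source trial, 10.b gives S_I changes of 7.4 − 4.5 = 2.9 and 4.5 − 4.2 = 0.3, a difference of 2.6. Treating the cells as equally weighted, f = 0.440 on the interaction scale implies an outcome SD of 2.6 / (4 × 0.440) = 1.48. On d/2 it implies an SD of change of 2.6 / 0.88 = 2.95. No SD is reported to choose between them. For the ratio itself, 10.b assumes a baseline of 46 but gives no SD for this population and no target difference. The ± values it quotes belong to preclinical AD cases and controls, and it does not say what kind of spread they are.

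**The case against.** The strongest reply is that nothing was miscalculated: the stated power follows from the stated inputs. That stands.

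It can also be said that a reader might infer from this section that the trial's real power is only 46–59%. The documents do not support that inference:

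- The text on the primary outcome never says that f is d/2, and the definition behind 0.440 is not given.
- Of the two d/f pairs actually printed, both for fMRI, one fits d/2 (1.25 and 0.626) and the other does not (1.34 and 0.8, where d/2 is 0.67). The fMRI calculations also used their own equations.
- The cognition paragraph names no test, sidedness or correlation, so its 0.81 may come from a different test. That explains the contrast without showing the primary figure to be wrong.
- The 46% is two-sided, whereas the plan is one-tailed.

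Two further replies have partial force. Lowering 0.440 to 0.3 is a real discount if both values are on the same scale, so *conservative* has some basis. And section 10.a calls the study an exploratory pilot, which limits the consequences. Neither removes the problem. A discount from an undefined value cannot be judged. Section 9 attaches the exploratory label to the secondary outcomes, while 2.a sets a demonstrative aim for the primary one.

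**Conclusion.** The point holds as a fault in how the power statement is scaled and described. The over-90% figure is correct for a between-arm difference in change of 1.2 outcome SD (1.10 SD of change), and 10.b presents that very large effect as modest. Across the section f is not used on one stated scale: 0.81 at f = 0.4 cannot sit beside over 90% at f = 0.3 under one method, which would give 99% at f = 0.4.

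The size of the issue is best expressed by what 20 per arm can detect with 80% power: about 0.80 SD of change one-sided, 0.91 two-sided. This rests on G*Power's default interaction formula, the plan's correlation of 0.4 for converting between SDs, and complete data on 40 participants. The 59% (or 52%) one-sided figure is conditional on 0.3 having meant d/2, which the documents neither state nor exclude.

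**What to change.** In section 10.b:

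- State that 20 per arm gives 92% power (F test; 96% one-sided) for a between-arm difference in change of 1.2 outcome SD, equal to 1.10 SD of change at correlation 0.4.
- State that under the one-tailed 0.05 test the difference detectable with 80% power is about 0.80 SD of change (0.91 two-sided).
- Give the assumed SD of the ratio and the target difference in ratio units, or say that they are unknown.
- State which definition of f the source value 0.440 uses, and name the test, sidedness and correlation behind the cognition figure of 0.81.
- Add, labelled as sensitivity and not as planned power, that if 0.3 was meant as d/2 (0.6 SD of change) power is about 59% one-sided, or 52% if the 0.6 is in outcome SD.
- Remove the descriptions of the effect as modest and the calculation as conservative, and the statement that greater power is likely, unless the definition of f supports them.

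The cost is wording and a less favourable stated figure. The sample size, design and analysis do not change.

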[name] is a Senior Research Fellow in the Laboratory of Neuroscience. She has completed her post-doctoral training in Neurosciences at University of California Los Angeles. She is also a licensed Nurse Practitioner and has practiced as a NP in the Johns Hopkins Neurology. [name] will be lead investigator on the protocol. She will be responsible for multiple clinical duties along with PI including overseeing participants' safety. She will obtain consent, conduct History and Physicals and perform LPs.

[name], MA, Ph.D. (LNS/NIA)

[name] is a Postdoctoral Fellow in the Human Neuroscience Unit under the training of [name]. He will be responsible for recruitment and contact with participants,

cognitive testing, MRI/fMRI/MRS, and data analysis. [name] has over 5 years of experience with neuropsych assessment and MRI research on patients with neurodegenerative diseases

12. Anticipated benefit

This pilot study of two short-term diets is not expected to generate direct benefits for the participant. While the diets are likely to decrease body weight and increase insulin sensitivity (i.e., decrease HOMA-IR), changes which may be desirable to the participants and their physicians, the changes are likely to be temporary. This is a short-term study and, therefore, the magnitude and duration of these effects and their impact on long-term health is unclear. The study will generate generalizable knowledge on the effects of short-term implementation of 5-2 CR.

13. Classification of Risk

13. a. For adults

Overall, we classify the study as greater than minimal risk.

13. b. For adults without consent capacity

Not applicable.

13. c. For children

Not applicable.

13. d. Overall risk and benefit consideration

The risks are reasonable in relation to anticipated benefit.

14. Consent Documents and Process

14. a. Designation of those obtaining consent

The principal investigator, clinical research coordinator (nurse) and NIA research nurses and nurse practitioners will be authorized to obtain consent. Investigators identified as being authorized to obtain consent in section 11.f. above will be allowed to obtain consent. In addition, NIA research nurses and nurse practitioners are qualified to obtain consent by their training and will also be authorized to obtain consent. All staff obtaining informed consent has completed the NIMH HSPU "Elements of Successful Informed Consent" training.

14. b. Consent procedures

All participants will receive a verbal explanation in terms suited to their comprehension of the purposes, procedures and potential risk of the study and of their rights as research participants. Participants will have the opportunity to carefully review the written consent form and ask questions regarding this study prior to signing. When the participant fully understands her responsibilities and possible risks and discomforts and agrees to participate in the current study they will be provided with the consent to sign. A signed copy will be provided to each participant, as well as placed in her medical record. No procedures will begin until the informed consent has been properly obtained.

In particular, the summary study design will be detailed. Furthermore, participants will be fully informed about the data and safety monitoring procedures.

14. c. Consent documents

Consent forms contain all required elements specific to the CNS IRB protocol template (rev 1.27.14). As stated, a consent document for healthy volunteers is submitted with this protocol. No special documents are needed.

15. Data and Safety Monitoring

15. a. Data and safety monitor

The Principal Investigator (PI) will be the data and safety monitor.

15. b. Data and safety monitoring plan

The PI will conduct periodic review of the data every at least 3 months to ensure that data are collected, saved and stored in a consistent manner and according to the Protocol. The PI will conduct periodic review of safety data (clinically significant lab results, H&P sessions, procedure notes, etc.) every at least 3 months, including review of expected AE's occurring more frequently than expected or at greater severity than expected.

15. c. Criteria for stopping the study or suspending enrollment or procedures

Temporary suspension of enrollment will occur if any related AE of grade 3 or higher occurs, in anticipation of its review by the NIA Clinical Director and the IRB. Study procedures for participants already enrolled may continue, unless otherwise instructed by the NIA Clinical Director and/or the IRB. The study may resume enrollment after the NIA Clinical Director and the IRB have given us permission to do so.

16. Quality assurance

16. a. Quality assurance monitor

The PI will be responsible for QA monitoring of this study. The PI will address any issues discovered. In addition the NIA Clinical Director may randomly review charts for Quality assurance.

16. b. Quality assurance plan

The PI will acquaint the research team with the basic principles of the ICH-GCP guidelines. The PI will ensure that the research team is following the protocol, complying with regulatory policies, and collecting and reporting data according to the protocol. The PI will delegate to an experienced research professional to conduct audit on 10-20% of participant's research charts once the participant has completed the study. In addition the Clinical Director may randomly review charts for quality assurance. The Quality Assurance designee will assess adherence to study procedures and timelines; review roles/responsibilities of research team members; clinical and research data collection; any AE or UPs. The PI will address any issues discovered.

17. Reporting of Unanticipated Problems, Adverse Events and Protocol Deviations

The Principal Investigator is responsible for detecting, documenting, and reporting unanticipated problems, adverse events (AEs), including serious adverse events (SAEs), and deviations in accordance with NIH policy, IRB requirements, and federal regulations. Relatedness to the research of all serious adverse events will be determined by the PI in consultation with the Clinical Director.

Serious unanticipated problems, serious adverse events (including deaths) that are not unanticipated problems, and serious protocol deviations will be reported to the IRB and CD as soon as possible and in writing not more than 7 days after the PI first learns of the event, unless immediate reporting is waived for specific serious adverse events as noted below. Not serious unanticipated problems and not serious deviations will be reported to the IRB and CD as soon as possible and in writing not more than 14 days after the PI first learns of the event. Written reports will be submitted in PTMS.

All adverse events, deviations, and unanticipated problems will be summarized and reported at the time of Continuing Review. The following expected adverse events will not be reported at the time of Continuing Review unless they occur at a severity or frequency greater than expected. Adverse events occurring at a greater severity or frequency than expected will be reported as Unanticipated Problems. These events include syncope or presyncope that occur during or after blood draws that may occur up

to 5% of the participants, laboratory values outside the normal range with no potential clinical significance that may occur up to 5% of the participants, or incidental findings on MRI that are non-life threatening and are not requiring further medically-indicated diagnostic testing or treatment that may occur up to 5% of the participants.

18. Alternatives to Participation

Subjects do not receive any treatment in this study or forego any treatment in order to participate in this study. The alternative, therefore, is not to participate.

19. Privacy

All research activities will be conducted in as private a setting as possible. All interactions will take place in private settings, limiting personnel present.

20. Confidentiality

20. a. For research data and investigator medical records

We will use hard copy case report forms to record clinical and research data, which will be kept in the participants' charts.

All hard copy research data and investigator medical records will be held at the nurse's station during the participant's visit and stored in a locked cabinet within a locked room when unoccupied. Biomarker levels, cognitive test results and MRS/fMRI images will be saved electronically on a secure NIA/NIH intranet with access limited to authorized NIA staff members and secure password protected NIA computers. All NIA members who have access to these databases have the proper training on participant confidentiality as well as the required Human Subject Protection Training.

When results of an NIA/NIH research study are reported in medical journals or at scientific meetings, the people who take part are not named and identified. The NIA/NIH will not release any information about the participant's research involvement without their written permission. However, if they sign a release form, for example, for an insurance company, the NIA/NIH will give the insurance company information from their medical record. This information might affect (either favorably or unfavorably) the willingness of the insurance company to sell them insurance.

In research collaborations all participants will be identified by a code rather than by their name. The results are research material and are strictly confidential. Information will not be released without the participant's consent, but may be reviewed by other researchers for scientific purposes.

All of the tests in this protocol are done for research purposes only. It is not our policy

to return research results to participants, however, if we find information that is important to the participant's health or well-being, we will return the results to them. In this event, participants will be referred to their private physician. If the participant requests a copy of lab results, those done under CLIA certification will be provided to the participant. For tests not done in a CLIA certified lab, including genetic results, referrals to CLIA certified labs in the participant's area will be provided. We are unable to pay for CLIA testing. The results or the scan from the MRI study will be provided to their physician with participants' written permission.

The genetic studies in this protocol are not done in a CLIA certified lab. We test for the APOE ε4 gene in this study, which increases the risk of Alzheimer's disease and cardiovascular disease, although it does not mean that whomever carries that gene will develop Alzheimer's disease or coronary artery disease. Participants who wish to know these results will meet with the principal investigator, who will consult them on the need for confirmation by a CLIA certified lab, and the significance of their particular genotype on AD and cardiovascular risk based on the literature. Genetic counseling will be available.

20. b. For stored samples

Biological samples (whole blood, plasma, serum, CSF, extracted DNA and RNA) will be stored at the NIA Core Lab or one of our licensed facilities and released to study investigators and collaborators by the Principal Investigator for analysis. Participants' names and identifying information will not be on the samples; samples will be identified by a code. The key to the code will be kept in a separate, secure area.

If a participant withdraws from this research project before it is complete, any samples obtained before she withdraws will be kept and her privacy will be protected.

20. c. Special precautions

Hard copy data/records will be locked within a cabinet inside of a locked room when occupied. Samples without identifiers will be in a single lock container. Electronic data will be stored on an encrypted, password protected NIH computer or encrypted NIH servers. Only study investigators will have access to the samples and data, as well as the NIA Clinical Director and IRB monitors or auditors as part of their supervisory duties.

Finally, de-identified results from clinical trials will be posted on [clintrials.gov](https://www.clinicaltrials.gov).

21. Conflict of interest

21. a. Distribution of NIH guidelines

NIH guidelines on conflict of interest have been distributed to all investigators.

21. b. Conflict of interest

There are no conflicts of interest to report.

21. c. Role of a commercial company or sponsor

There is no commercial company or sponsor for the study.

22. Technology transfer

The authors entered into a technology transfer agreement with [name] of the University of California – San Francisco for the utilization of the software EXAMINER.

23. Research and Travel Compensation

All participants will be compensated for their time and research-related inconveniences via NIA debit cards. Payments will be given as stated below. Compensation will typically be prorated for parts completed if the participants do not complete the study.

Participants will be compensated for each visit as follows:

Screening	\$50
Baseline	\$350
Week # 2 Visit	\$150
Week # 4 Visit	\$150
Week # 6 Visit	\$150
Week # 8 Visit	\$500

Total compensation will be \$1,350 for participants that complete the study. If they do not complete the study or if the study physician needs to extend their participation due to a missed visit, they will be paid for those parts completed; blood draw \$20, Mixed Meal Test (MMT) \$50, MRI \$50, lumbar puncture \$150, cognitive testing \$20, calorie restriction for one week \$50, accelerometer \$10/day to wear.

Participants will be offered a meal on the Screening Visit, Baseline Visit, and Outcome Visit.

No travel or lodging compensation is provided, because all subjects will be recruited from the greater Baltimore area. No escort fee will be provided.

24. References

1. Kapogiannis, D. & Mattson, M.P. Disrupted energy metabolism and neuronal circuit dysfunction in cognitive impairment and Alzheimer's disease. *Lancet neurology* **10**, 187-198 (2011).
2. Goldstein, B.J. Insulin resistance as the core defect in type 2 diabetes mellitus. *Am J Cardiol* **90**, 3G-10G (2002).
3. Schrijvers, E.M., et al. Insulin metabolism and the risk of Alzheimer disease: the Rotterdam Study. *Neurology* **75**, 1982-1987 (2010).
4. Cersosimo, E. & DeFronzo, R.A. Insulin resistance and endothelial dysfunction: the road map to cardiovascular diseases. *Diabetes Metab Res Rev* **22**, 423-436 (2006).
